6.2.15 Length of Stay in Hospital and Intensive Care Unit

The length of stay in hospital and ICU in days after PEA during Visit 3 will be reported for each patient.

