7.2 Secondary Efficacy Endpoints

The secondary efficacy endpoints for the study are mentioned below.

1. PVR (6 months after PEA): percent change from baseline in PVR at Visit 4.

PVR assessment at Visit 4 will use the nominal visit information collected in eCRF without considering the time window because PVR status is expected to be stable after PEA.
2. Composite clinical endpoints (6 months after PEA), including patients with any one of the following clinical endpoints, from immediately after PEA to Visit 4.
 - All-cause death

All deaths that happen after randomisation until the date of Visit 4, 6 months after the PEA, will be included.
 - PH-related hospitalisation

All PH-related hospitalisation except the in-hospital care after PEA from randomisation until 6 months after PEA will be included.

- Need for PAH-targeted therapy

All PAH-targeted therapy from randomisation until 6 months after PEA will be included.

- Functional class unchanged or worse

When comparing the functional class assessment at Visit 1 with the functional class assessment at other visits, the same class will be defined as unchanged, and a higher class will be defined as worse. The worst case after treatment will be used.

3. Perioperative findings at Visit 2:

- Circulatory arrest time
- Surgery-related complications (Section 6.2.7)

4. Surgical evaluation of specimen (difficulty to withdraw obstructive material):

- Ease of dissection plane, classed as easier than normal (1), normal (2), more difficult than normal (3)
- Completeness of disease clearance, classed as better than expected (1), as expected (2), worse than expected (3)
- Both clot and vessel wall will be measured as score of 1 to 3 with the following scores: more solid than usual (1), normal (2) more friable than usual (3).

Surgical evaluations of specimen are from perioperative measures. The data will be treated as an ordinal response. A higher score means a worse case.

5. All-cause death

All deaths that happen during the whole course of the study will be included.

6. Withdrawal during randomised treatment phase

Only withdrawals after randomisation but before PEA will be included.

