3.2.2. Secondary Efficacy Endpoints

The secondary efficacy endpoints for the study are mentioned below.

1. PVR (6 months after PEA): percent change from baseline in PVR at Visit 4.
2. Composite clinical endpoints (6 months after PEA), including patients with any one of the following clinical endpoints, from randomisation to Visit 4.
 - All-cause death
 - PH-related hospitalisation
 - Need for PAH-targeted therapy
 - Functional class unchanged or worse
3. Perioperative findings at Visit 2:

- Circulatory arrest time
- Surgery-related complications (Appendix 13.3)

4. Surgical evaluation of specimen (difficulty to withdraw obstructive material):
 - Ease of dissection plane
 - Completeness of disease clearance
 - Clot and vessel wall
5. All-cause death
6. Withdrawal during randomised treatment phase

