8.2.2. Composite Clinical Endpoints

Composite clinical endpoints from randomisation to Visit 4 will be tabulated by treatment group containing the number and percentage of patients with an event as well as the number of event for the PEA set and the PPS. The Fisher exact test will be utilised to test the proportion difference along with the Clopper-Pearson exact CI when applicable. For analysis based on the ordinal response of functional class, the row mean score from the Cochran Mantel-Haenszel test will be used to test the response difference between groups.

Composite clinical endpoints include following clinical endpoints:

- All-cause death

All deaths that happen after randomisation until the date of Visit 4, 6 months after the PEA, will be included.

- PH-related hospitalisation

All PH-related hospitalisation except the in-hospital care after PEA from randomisation until 6 months after PEA will be included.

- Need for PAH-targeted therapy

All PAH-targeted therapy from randomisation until 6 months after PEA will be included.

- Functional class unchanged or worse

When comparing the functional class assessment at Visit 1 with the functional class assessment at other visits, the same class will be defined as unchanged, and a higher class will be defined as worse. The worst case after treatment will be used.

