9.5. Physical Examination

A complete physical examination including assessments of the head, eyes, ears, nose, throat, skin, neck (including thyroid), lungs, cardiovascular system, abdomen, lymph nodes, and extremities will be obtained at screening. A physical examination including updates since the screening visit with focus on previously noted abnormalities in organ systems, including skin and hair, will be completed at time points specified in Schedule of Events.

Physical examination data will be summarised by treatment group and body system with number and percentage of patients.

Physical examination results for all patients will be presented in a listing.

10. Interim Analysis

A data safety monitoring board (DSMB) will review unblinded safety data throughout the study and make recommendations as appropriate. Further details are specified in the DSMB charter.

11. Changes in the Planned Analysis

The changes for the statistical analyses from the protocol to this SAP are stated below:

1. The analysis set to be used for perioperative endpoints (Circulatory Arrest Time, Surgery-related Complications, Surgical Evaluation of Specimen, PEA hospital length of stay, PEA ICU length of stay, Time on mechanical ventilation, In-hospital mortality) have been updated to PEA set only, with the consideration that these endpoints are peri-PEA surgery related endpoints and it makes more sense to narrow down the patients to those who have undergone PEA surgery only.
2. The analysis sets to be used for postoperative endpoints (Percent Change in PVR from baseline to Visit 4, Composite clinical endpoint from baseline to Visit 4, NT-proBNP, cardiac output, cardiac index, mRAP, mPAP, PAWP change from baseline to Visit 4, Functional class at Visit 4, All-cause death, Need for PAH-targeted postoperative therapy at Visit 4) have been updated to PEA set and PPS, with the consideration that the endpoints are post-PEA surgery endpoints, and it makes more sense to restrict the analysis to patients who undergone PEA surgery; PPS will be used since those per-protocol patients need to be considered as a complementary analysis set.

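### The composite labelled 6 months after PEA scores functional class by the worst visit, so a patient unchanged at early post-operative Visit 3 is an event even if improved at Visit 4

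*SAP*

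**What the plan says.** SAP 3.2.2 defines the endpoint as "Composite clinical endpoints (6 months after PEA), including patients with any one of the following clinical endpoints, from randomisation to Visit 4". The protocol (7.2) has the shorter window, "including patients with any one of the following clinical endpoints, from immediately after PEA to Visit 4"; SAP section 11, change 4, declares the move to randomisation as the starting point.

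For the functional-class component, SAP 8.2.2 and protocol 7.2 use the same rule. It works by "comparing the functional class assessment at Visit 1 with the functional class assessment at other visits"; the same class is unchanged, a higher class is worse, and either is an event. Where visits differ, "The worst case after treatment will be used".

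The schedules of events (protocol Table 12-1, SAP 13.1) collect WHO class at every visit: Visit 2 (before PEA, Day 90+30), Visit 3 (post-PEA, Day 96) and Visit 4 (Day 276±10). Protocol 6.2.15 places Visit 3 in the surgical admission: "The length of stay in hospital and ICU in days after PEA during Visit 3 will be reported for each patient".

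The composite is tested with the Fisher exact test. SAP 8.2.2 adds a second test: "For analysis based on the ordinal response of functional class, the row mean score from the Cochran Mantel-Haenszel test will be used". It does not say which visit supplies the class.

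**The concern.** A reader who sees a composite labelled as 6 months after PEA will take its functional-class part as the patient's class at six months. The scoring rule does something else: one visit without improvement is enough, and one of the visits that count falls in the recovery from major surgery. A patient in class III at Visit 1, still III at Visit 3 and I at Visit 4 is recorded as a failure.

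Two gaps in the text add to this. The SAP defines a treatment period (Day 1 to Day 90) but does not tie the words after treatment to it, so two programmers could disagree about Visit 2. The Cochran-Mantel-Haenszel test cannot be run without an unstated choice of visit. What is at stake is the meaning of the composite result and of that test.

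**Working it through.** **Which visits count.** The last dose is given on the morning of PEA (SAP 3.1), so:

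- After the first dose, with the SAP window from randomisation: Visits 2, 3 and 4.
- After the last dose, or after PEA: Visits 3 and 4.
- Protocol window (from immediately after PEA): Visits 3 and 4.

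Visit 3 is in every list. Visit 2 enters only if the SAP window applies and after treatment also means after the first dose.

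**Timing.** Day 276 − Day 96 = 180 days between Visits 3 and 4.

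**Patterns.** Class relative to Visit 1 can be improved, unchanged or worse. Among patients improved at Visit 4 there are 3 × 3 = 9 patterns over Visits 2 and 3:

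- Visit 4 only: 0 of 9 are events.
- Visits 3 and 4: 2 × 3 = 6 of 9 are events.
- Visits 2, 3 and 4: 9 − 1 = 8 of 9 are events.

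These count patterns, not patients.

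**Effect on the comparison between arms (illustration).** The plan gives no rate, effect size or power for this endpoint, so there is no figure to reproduce. From the documents: a target of 80 completers (protocol 4.3.3) with 1:1 allocation, hence 40 per arm, and a two-sided 5% level. Assumed: v, the composite rate with class read at Visit 4, and e, the share not improved at Visit 3. If the two are independent, the rate under the worst-visit rule is

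1 − (1 − e)(1 − v),

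and with equal e in both arms the difference becomes (1 − e) × (difference at Visit 4). Fisher power is by exact enumeration of both binomials.

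| v, arm 1 vs arm 2 | e, arm 1 vs arm 2 | Worst-visit rates | Difference (points) | Power |
|---|---|---|---|---|
| 10% vs 35% | Visit 4 only | 10.0% vs 35.0% | 25.0 | 72% |
| 10% vs 35% | 30% in both | 37.0% vs 54.5% | 17.5 | 29% |
| 10% vs 35% | 50% in both | 55.0% vs 67.5% | 12.5 | 15% |
| 10% vs 35% | 80% in both | 82.0% vs 87.0% | 5.0 | 6% |
| 10% vs 35% | 30% vs 50% | 37.0% vs 67.5% | 30.5 | 74% |
| 10% vs 20% | Visit 4 only | 10.0% vs 20.0% | 10.0 | 16% |
| 10% vs 20% | 30% in both | 37.0% vs 44.0% | 7.0 | 7% |
| 10% vs 20% | 30% vs 50% | 37.0% vs 60.0% | 23.0 | 48% |

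For the fifth row: 0.70 × 0.90 − 0.50 × 0.65 = 0.630 − 0.325 = 0.305.

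Independence matters too. If Visit 3 and Visit 4 events overlap fully, the rate is the larger of e and v. With v at 10% vs 35% and e equal at 30%, the rates are 30% vs 35% and power is 5%; at 50% or 80% the difference is zero.

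**The case against.** The strongest reply is that the worst-visit rule is a deliberate, pre-specified choice. It appears in both documents, and the composite is cumulative: death, PH-related hospitalisation and PAH-targeted therapy all accumulate over the window, so a worst-visit class fits that pattern. The label and the window stand in one sentence, and the label can be read as the end of the window. Class at each visit, with shift tables, is reported anyway (SAP 8.3). Much of this stands. The window from randomisation is declared and is not disputed here, and the separate tables limit the harm. But the other components are adverse events whenever they happen, whereas an unchanged class shortly after surgery is not a failure at six months. The shift tables do not change what the Fisher test of the composite tests.

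A reader might infer four stronger points that the documents do not support.

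- *The rule must weaken the comparison.* It does so if early rates are equal in both arms. The table shows that unequal early rates can preserve or enlarge the difference, and the documents give no class rates for this population.
- *The hospitalisation rule shows that Visit 3 was meant to be left out.* That rule reads "All PH-related hospitalisation except the in-hospital care after PEA from randomisation until 6 months after PEA will be included". All patients who undergo PEA have in-hospital care afterwards, so without the exclusion it could count for all of them. Functional class has no such built-in event.
- *SAP section 11 implies Visit 4 only.* It justifies the analysis sets "with the consideration that the endpoints are post-PEA surgery endpoints", but Visit 3 is itself post-PEA. The phrase bears only on Visit 2.
- *Visit 2 always counts under the SAP window.* It does not if after treatment means after study drug ends.

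**Conclusion.** The point holds as a problem of definition and interpretation, and should be fixed. On every reading of the rule, a patient unchanged at Visit 3 and improved at Visit 4 is an event, so the functional-class component is not 6-month status. This rests on the text and the visit schedule alone.

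The consequence for the arm comparison is not established in either direction. The power figures rest on assumed rates, on independence or full overlap of the visits, and on 40 per arm. The trial was not sized on power (SAP 4.1).

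The reach is narrow: one exploratory secondary endpoint and one test without a named visit. All-cause death and post-PEA need for PAH-targeted therapy are also analysed separately (SAP 8.2.5, 8.3), and the primary PVR analysis is unaffected.

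**What to change.** Amend SAP 8.2.2, with an entry in SAP section 11 recording the departure from protocol 7.2, before unblinding:

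1. Define the component as WHO functional class at Visit 4 unchanged or worse than at Visit 1.
2. Use the same Visit 4 assessment for the Cochran-Mantel-Haenszel test.
3. State how living patients with no Visit 4 class are counted, for example as events, with a sensitivity table that excludes them.
4. Keep the worst-visit version as a sensitivity table that names the visits it uses.
5. State in SAP 3.2.2 that death, PH-related hospitalisation and PAH-targeted therapy accumulate from randomisation to Visit 4, while functional class is taken at Visit 4.

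The cost is a short edit by the route already used for changes 4 and 5, with no new data. The downside is that transient worsening or lack of improvement before Visit 4 no longer counts through this component in the main version, and that the missing-data rule in item 3 becomes necessary.

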8.2.3. Perioperative Findings

8.2.3.1. Circulatory Arrest Time

Circulatory arrest time (minute) at Visit 2 from perioperative findings will be tabulated by treatment group using the descriptive statistics for the PEA set. An analysis of variance (ANOVA) will be employed to compare the mean difference between 2 groups. P-value from Shapiro-Wilk test will also be presented in this table to indicate the normality of this variable. In case normality assumption cannot hold, the Wilcoxon rank-sum test should be considered.

8.2.3.2. Surgery-related Complications

Surgery-related complications at Visit 2 from the perioperative findings will be tabulated by treatment group in a descriptive way for the PEA set, presenting the number and percentage of patients for each symptom. The Fisher exact test will be utilised to test the proportion difference along with the Clopper-Pearson exact CI.

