4.3.3 Replacements

A total of 88 patients will be randomly assigned in the study with a target of 80 patients completing the study with an assumption of a 10% dropout rate.

Therefore, drop out for any reason before the last follow-up visit (Visit 4) will be monitored continuously throughout the study, and patients that drop out will be replaced to make a total number of 88 randomised patients. In case of a high initial dropout rate, the DSMB and the sponsor will evaluate the reasons for drop out and decide in mutual agreement on potential extension of further randomisations.

5 Study Drugs

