6.6 Sample Collections

All visits that include clinical laboratory safety assessments must be after an 8-hour fast.

Sample collection, processing, and shipping should be performed according to the central/local laboratory requirements.

7 Statistical and Analytical Plan

Due to the investigative nature of this study, all statistical analyses will be exploratory. A clearly defined statistical analysis plan (SAP) will be generated separately to provide a more detailed description of the planned statistical analyses in order to meet the objectives of the registry. The SAP will be finalised before database lock and the breaking of the study blind. Further specific analyses for publications will be prespecified in separate plans or documents.

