7.8.2 Analysis of Secondary Efficacy Endpoint

For the secondary endpoint, percent change from baseline in PVR at Visit 4, the same approach as in the primary analysis will be used.

Composite clinical endpoints at 6 months after PEA will be tabulated by treatment group containing the number and percentage of patients with an event as well as the number of event. The Fisher exact test will be utilised to test the proportion difference along with the Clopper-Pearson exact CI when applicable. For analysis based on the ordinal response of functional class, the row mean score from the Cochran-Mantel-Haenszel test will be used to test the response difference between groups.

Circulatory arrest time from perioperative findings will be tabulated by treatment group using the descriptive statistics. An analysis of variance may be employed to compare the mean difference between 2 groups. In case normality assumption cannot hold, the Wilcoxon rank-sum test should be considered.

Surgery-related complications from the perioperative findings will be tabulated by treatment group in a descriptive way, presenting the number and percentage of patients for each symptom.

For surgical evaluation of specimen endpoints, ease of dissection plane and completeness of disease clearance will be tabulated by treatment group containing the number and percentage of patients in each level. The Cochran-Mantel-Haenszel test will be used to test the ordinal response difference between groups if deemed necessary.

Clot and vessel wall friability, measured as more solid than usual, normal, or more friable than usual, will be tabulated by treatment group containing the number and percentage of

patients in each level. The Cochran-Mantel-Haenszel test will be used to test the ordinal response difference between groups if deemed necessary.

All-cause death during the whole study course and withdrawal during the randomised treatment phase will be tabulated by treatment group containing the number and percentage of patients with event. Time to death will be analysed using the Kaplan-Meier method.

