- When frequency counts are presented, the percentage will be suppressed when the count is zero in order to draw attention to the non-zero counts. A row denoted “Missing” will be included in count tabulations where specified on the shells to account for dropouts and missing values. Percentages will be based on the total number of patients in the respective analysis set unless otherwise specified.
- Unless otherwise specified, statistical tests will be 2-sided and performed using a 5% significance level, leading to 95% (2 sided) confidence intervals (CIs). Modelling techniques will be used in an exploratory sense. No adjustments for multiplicity are made.
- Partial dates will be imputed based on the rules specified in Appendix 13.4.
- All laboratory data will be reported by using the International System of Units.
- Unless otherwise specified, the baseline will be defined as the last valid assessment, including assessments from the unscheduled visit, prior to the study drug administration.
- A Visit 2 assessment is considered as valid only when the assessment is completed within 7 days prior to PEA. For assessments at Visit 4, the nominal visit collected in electronic case report form (eCRF) will be used in the analysis. This rule is applicable to all endpoints derived by the visit.
- By-patient listings will be created for each eCRF module for all screened patients. Patients will be identified in the listings by patient number. If data are to be summarised by visit, the visit name collected on the eCRF page will be used.
- All analyses will be conducted using SAS® software Version 9.3 or later (SAS Institute Inc, Cary, North Carolina).

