4.1. Sample Size

A total of 88 patients, accounting for a 10% dropout rate, will be randomly assigned into riociguat or placebo groups at a ratio of 1:1 in the study. The sample size for this study is not based on the required statistical power to test any specific hypothesis but feasibility to initially assess the safety and efficacy of riociguat on preoperative pulmonary haemodynamics in patients with operable CTEPH.

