13.3. Surgery-related complications

Surgery-related complications are defined as the following:

- Bleeding and/or blood loss >1 L in 12 hours
- Airway bleed with need for extracorporeal membrane oxygenation
- Any use of extracorporeal membrane oxygenation for respiratory or haemodynamic support, specified as veno-venous or veno-arterial
- Prolonged ventilation >96 hours
- Need for tracheostomy
- Need for drainage of pericardial effusion
- Neurological complications, ie, stroke, cerebral, subdural bleeding
- Reintubation or noninvasive ventilation for reperfusion response
- Haemoptysis requiring any intervention
- Renal failure requiring dialysis
- Wound infections
- Pneumonia
- Prolonged need for inotropic support (≥ 5 days)

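### SAP 8.2.3.2 adds an undeclared Fisher test, by natural reading one for each of 13 complications, and plans no patient-level total, so the surgery-related complications endpoint is never compared as a whole

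*SAP*

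**What the plan says.** Protocol 7.8.2 states: "Surgery-related complications from the perioperative findings will be tabulated by treatment group in a descriptive way". It asks for numbers and percentages per symptom and names no test. The same section does name tests for neighbouring endpoints: Fisher for the clinical composite, analysis of variance or Wilcoxon for circulatory arrest time, and Cochran-Mantel-Haenszel for the specimen scores.

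SAP 8.2.3.2 keeps the descriptive table, restricts it to the PEA set, and adds a test with a Clopper-Pearson interval: "presenting the number and percentage of patients for each symptom. The Fisher exact test will be utilised to test the proportion difference".

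SAP Section 11 lists the changes from the protocol. It mentions surgery-related complications once, for the move to the PEA set. The added test is not there.

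The definition (Protocol 6.2.7, SAP 13.3) has 13 items. One is an airway bleed needing extracorporeal membrane oxygenation (ECMO). Another is "Any use of extracorporeal membrane oxygenation for respiratory or haemodynamic support", which contains it.

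On error control, SAP Section 4 says that "statistical tests will be 2-sided and performed using a 5% significance level" and that "No adjustments for multiplicity are made". Protocol Section 7 says that "all statistical analyses will be exploratory".

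**The concern.** A secondary objective is the effect of riociguat on safety and efficacy aspects during PEA, and the rationale is that better haemodynamics before surgery could reduce surgical morbidity. Surgery-related complications are the endpoint closest to that idea. The SAP tests them only in pieces. It has no row for patients with at least one complication and no count per patient, although it plans patient-level totals for the clinical composite (8.2.2) and for treatment-emergent adverse events (9.1.1).

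Two things follow. Tests on uncommon single items in a trial of this size can detect very little. And 13 p-values, one pair of which can be driven by the same event, give some chance that an isolated item is reported as significant when nothing is going on. Because the test is missing from Section 11, a reader of the final report could not tell that the protocol had left this table without p-values.

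**Working it through.** **Group size.** The SAP plans "A total of 88 patients, accounting for a 10% dropout rate"; Protocol 4.3.3 works "with a target of 80 patients completing the study with an assumption of a 10% dropout rate". 80 × 1.10 = 88 reproduces the stated number (80 / 0.90 = 88.9, rounded up to 89, is the other convention). With 1:1 allocation this means 40 per arm for completers and 44 per arm randomised. I use 40 and give 44 for comparison.

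**Nominal ceiling.** Thirteen independent tests at 0.05 give 1 − 0.95^13 = 0.487, with 13 × 0.05 = 0.65 false positives expected. Fisher's test is conservative with small counts, so the attained figure is lower.

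**What one test needs.** With no event in one arm of 40, the two-sided p-value for k events in the other is 2 × C(40,k) / C(80,k). For k = 5 this is 2 × 658,008 / 24,040,016 = 0.055. For k = 6 it is 2 × 3,838,380 / 300,500,200 = 0.026. A split of at least 6 to 0 is needed.

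**Attained size and family-wise error.** The documents give no complication rates, so all rates here are assumptions. With a common true rate for all items and independence, the size s of one test comes from enumerating both binomials, and the family-wise error is 1 − (1 − s)^13 (s shown rounded), at 40 per arm:

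| True rate | Size of one test | At least one of 13 |
|---|---|---|
| 2% | 0.0001 | 0.002 |
| 5% | 0.0040 | 0.051 |
| 10% | 0.0168 | 0.197 |
| 15% | 0.0255 | 0.285 |
| 20% | 0.0282 | 0.311 |

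At 44 per arm the last column is 0.067 at 5%, 0.225 at 10% and 0.283 at 20%.

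**Mixed rates with correlation.** Simulated with a one-factor model, correlation 0.3, 40 per arm, no effect; chance of at least one p-value at or below 0.05:

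- mostly rare (six items at 3%, four at 5%, then 8%, 10% and 15%): about 7%
- spread over 3-15%: about 15-17%
- those rates doubled: 24-27%, depending on the run

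Stronger correlation lowers these figures only moderately. For a mix of 5-20% rates, the figure is 0.194 under independence and 0.166 at correlation 0.6.

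**Power of a single item to detect a halving**, exact, 40 per arm: 0.5% for 5% v 2.5%, 4% for 10% v 5%, and 10% for 15% v 7.5%.

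**One patient-level comparison.** Take the 3-15% rates. If every rate is halved, the proportion with at least one complication goes from about 53% to about 33-34%, and Fisher's test on it has 35% power. Its attained type I error is about 3%. The set of 13 tests flags at least one item about as often under that benefit (36%), but also in about 17% of trials with no effect. The gain is therefore one interpretable comparison at low error, rather than more detections. If only the four commonest items are halved, power for the any-complication test falls to 9%.

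**The case against.** The strongest reply is that nothing was hidden about error rates. Both documents disclaim multiplicity adjustment, the protocol calls every analysis exploratory, and the sample size rests on feasibility. Low power and unadjusted p-values on a secondary endpoint are then the declared design, and Protocol 7.8 leaves details of methods to the SAP. This stands. A reader might infer that an error-control commitment has been broken, but the documents make none for this endpoint.

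A reader might also infer that the plan will produce spurious findings, perhaps at the nominal 49%. The documents do not support that. They give no rates, Fisher's test is conservative, and if most items are rare the family-wise error is close to 5%.

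A third inference would be that perioperative safety gets no patient-level answer at all. That is too strong. The SAP also reports patients with any adverse event and with serious events over V0 to V3, grouped haemorrhage, haemoptysis and stroke, in-hospital mortality, ICU stay and ventilation time. By-patient listings would allow a total to be derived later. None of these, however, is a prespecified comparison of the endpoint itself.

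Finally, the SAP does not say that the test is run on each item. That is inferred from the proportions it tabulates. If something else was meant, the tested variable is undefined, which also needs repair. Only one nested pair is clear from the list.

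Disclosure of unadjusted testing does not explain why a test was added to a descriptive table, why Section 11 omits it, or why the total is missing.

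**Conclusion.** The point holds as a discrepancy between documents and a gap in the analysis. SAP 8.2.3.2 adds a test that Protocol 7.8.2 does not have, Section 11 does not declare it, and the secondary endpoint has no patient-level comparison. These facts do not depend on any assumed rate.

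The size does depend on assumed rates. At 40 per arm, single items have 0.5% to 10% power to detect a halving from base rates of 5% to 15%. The chance of at least one false positive runs from about 7% (mostly rare items) through 15-17% (3-15%) to about 25% (doubled). The two problems trade off: where items are rare, chance findings are few and power is almost nil; where they are common, chance findings become the larger concern. The change should be made, but the trial's main conclusions do not rest on it.

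**What to change.** In SAP 8.2.3.2:

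- Make the proportion of PEA-set patients with at least one surgery-related complication the single comparison, with Fisher's test and a risk difference.
- Name a 95% CI method meant for a difference. Clopper-Pearson gives an interval for one proportion.
- Show the 13 items as counts and percentages without p-values, as the protocol does.
- If a count per patient is shown, keep it descriptive and count an event that meets two items once.

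In SAP Section 11, record the added comparison and its reason.

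A formal test on the count is not needed: an unweighted count ranks a wound infection with a stroke, and whether to accept that is a matter of judgement.

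The cost is SAP wording and an extra table row from data already collected. The downside is that a composite of items of unequal severity can dilute an effect confined to a few of them, as the fall from 35% to 9% power shows. The item table should therefore stay beside it.
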